### **Demographics/patient specifics:**

Age, sex, medical co-morbidities, weight, height, pre-treatment pain scores, BMI

**Primary outcome measure:** Post-treatment VAS score averaged daily over 4 weeks.

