**Title:** Effect of Topical Chylobinoid Cream on Pain and Function Scores for Hallux Disorders: A Randomized Controlled Trial

**Purpose:** The purpose of this study is to compare the change in pain scores in patients with hallux rigidus and hallux valgus who are treated with topical cannabidiol cream vs. placebo.

**Hypothesis:** Patients treated with topical 1.5% chylobinoid cream (chylobinoid is approximately 85% magnesium-cannabidiolic acid or Mg-CBDa, 5% CBD, 5% other cannabinoids, and naturally occurring plant lipids in a neutral emollient) will show improvement in hallux pain compared to those patients treated with placebo.

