# Patients and protocols:

Patients will be recruited from the practices of a fellowship trained Orthopedic Foot and Ankle surgeon at Rush University Medical Center. Patients with a new diagnosis of hallux valgus or hallux rigidus without prior operative intervention on the first metatarsal will be approached for enrollment in the study. Pre-treatment VAS pain scores and the Foot Function Index (FFI) are collected as a routine question on new patient questionnaires. Patient's with a VAS pain score of < 4 will be excluded. The goal of the intervention is to improve pain, and patient's with minimal pain at presentation have a little possibility of showing therapeutic response.

Enrolled patients will be randomized to receive chylobinoid cream vs. placebo cream (neutral emollient containing no active agent) for topical treatment of hallux rigidus or hallux valgus. Patients and treating physician will be blinded to the intervention. Patients will not be charged nor will their insurance be billed for cost of the chylobinoid cream or placebo cream. Patients will be instructed to apply the topical cream as needed for pain for a total duration of four weeks. This topical treatment will be combined with other commonly employed conservative modalities, including physical therapy and orthotics as clinically indicated. Patient's will receive the FFI survey via email weekly for a total of 4 weeks after treatment initiation. Patient's will be instructed to keep track of daily VAS pain scores in a pain journal for the four weeks of treatment.

Patient's will attend their regularly scheduled four weeks follow up clinic visit. Post-treatment VAS pain score will be collected at that visit, along with their daily pain journal. Patients will fill out a brief survey regarding their experience with the treatment. The remaining chylobinoid cream will be collected from patients and weighed in order to assess the amount of product used during the four-week study period. The difference in pre and post-treatment VAS score and FFI will be determined between the chylobinoid and placebo groups.

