### Sample Size:

Power analysis was preformed using a retrospective review of internal patients with new hallux rigidus and hallux valgus diagnoses. VAS scores at the time of presentation were determined. VAS score at presentation for hallux rigidus was 6.74 with standard deviation of 1.7. VAS score at presentation for hallux valgus was 6.45 with standard deviation of 1.68. A clinically significant improvement in VAS pain score was defined as a 2-point decrease. Power analysis based on 80% power and alpha of .05 for detection of a 2-point decrease in VAS score determined the study would require 12 patients with hallux rigidus per group (24 total) and 12 patients with hallux valgus per group (24 total). In order to account for 20% loss to follow up, a total of 28 patients will be enrolled for each hallux rigidus and hallux valgus group (56 total patients for the entire study).

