### **Secondary outcome measures:**

- 1. Pre- to post-treatment difference in VAS score
- 2. Pre- to post-treatment difference in FFI
- 3. Post-treatment FFI at different time points (1, 2, 3, and 4 weeks post treatment)
- 4. Adherence to treatment
- 5. Amount of Chylobinoid cream vs. Placebo cream used during the study period
- 6. Do you believe you received the treatment or placebo? (4 weeks)
- 7. Did the cream we gave you help with your pain? (4 weeks)

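### The four-week mean of daily VAS is labelled primary, but the purpose, the stated comparison and the 2-point target are not tied to it, and the stated pre/post difference gives up precision

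*Protocol*

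**What the plan says.** The Protocol uses VAS pain in five places.

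- **Purpose (opening statement):** "The purpose of this study is to compare the change in pain scores in patients with hallux rigidus and hallux valgus", cream against placebo. The object is change.
- **Patients and protocols:** patients are to "keep track of daily VAS pain scores in a pain journal for the four weeks of treatment". At the four-week clinic visit, "Post-treatment VAS pain score will be collected at that visit, along with their daily pain journal". The only between-arm comparison of pain described there is: "The difference in pre and post-treatment VAS score and FFI will be determined between the chylobinoid and placebo groups".
- **Sample Size:** from a retrospective review of the centre's own patients, "VAS scores at the time of presentation were determined", with SDs of 1.7 (hallux rigidus) and 1.68 (hallux valgus). The target is given as follows: "A clinically significant improvement in VAS pain score was defined as a 2-point decrease". At 80% power and alpha 0.05 this leads to 12 per arm within each diagnosis, and to 28 enrolled per diagnosis after an allowance for 20% loss.
- **Primary outcome measure:** "Post-treatment VAS score averaged daily over 4 weeks".
- **Secondary outcome measures, item 1:** "Pre- to post-treatment difference in VAS score".

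**The concern.** The outcome labelled primary is not the one that the rest of the Protocol describes. The purpose speaks of change. The procedures describe a between-arm comparison of a pre/post difference, which matches secondary outcomes 1 and 2. No procedure text says that the arms will be compared on the four-week mean.

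One name also covers two measurements. Under Patients and protocols, *post-treatment VAS* is a single reading at the clinic visit, handed in alongside the journal. Under Primary outcome measure it is the average of the daily scores. Secondary outcome 1 does not say which it uses.

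Two things are at stake. First, the visit score and the four-week mean have different SDs, and they share the same expected between-arm difference only if the full effect is present from the first day. The meaning of the 2 points for the labelled primary therefore cannot be read from the Sample Size section. Second, the comparison that is written down makes no use of presentation VAS beyond subtracting it. In a trial of about 11 evaluable patients per arm and diagnosis, that can cost noticeable precision.

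**Working it through.** **1. Reproducing the plan's figure.** Inputs from Sample Size: difference 2, SD 1.7, power 80%, alpha 0.05 (taken as two-sided).

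n per arm = 2 × ((1.960 + 0.842) × 1.7 / 2)² = 11.34, rounded up to 12.

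SD 1.68 also gives 12. The stated 12 is therefore what a two-arm comparison of one score gives when the presentation SD is used. By the t distribution the requirement is 13, and 12 per arm gives 78.6% power. Neither the SD of a change nor the SD of a four-week mean enters.

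**2. Patients available.** 28 per diagnosis is 14 per arm. After 20% loss, 14 × 0.8 = 11.2, taken as 11. Pooled over the two diagnoses this is 22 per arm.

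**3. Precision of the stated comparison.** Assumptions: true difference 2, SD 1.7 both at presentation and at follow-up, baseline/follow-up correlation ρ of 0.3, 0.5 or 0.6. The Protocol gives no correlation.

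- Unadjusted change: SD = 1.7 × √(2(1 − ρ)) = 2.01 / 1.70 / 1.52
- Follow-up score alone: SD = 1.70
- Adjusted for presentation VAS: residual SD = 1.7 × √(1 − ρ²) = 1.62 / 1.47 / 1.36

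Power, two-sided 0.05, noncentral t:

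| Comparison | 11 per arm, ρ = 0.3 / 0.5 / 0.6 | 22 per arm (pooled), ρ = 0.3 / 0.5 / 0.6 |
|---|---|---|
| Unadjusted change | 60 / 75 / 83% | 90 / 97 / 99% |
| Follow-up score alone | 75% | 97% |
| Adjusted, by formula | 78 / 86 / 90% | 98 / 99 / 99.7% |
| Adjusted, by simulation | 76 / 84 / 89% | 98 / 99 / 99.7% |

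The simulated row allows for chance baseline differences between the arms and is the one to rely on. The ratio of the variance of unadjusted change to the adjusted variance is 2/(1 + ρ) = 1.54 / 1.33 / 1.25.

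**4. Effect of the entry rule.** Only patients with VAS of 4 or higher enter. The Protocol does not say whether the retrospective SD was already restricted in this way. If it was not, cutting a normal distribution with mean 6.6 and SD 1.7 at 4 gives a baseline SD near 1.50. With the follow-up SD kept at 1.7 and the same correlations, unadjusted change then has 65 / 79 / 87% power at 11 per arm. The adjusted figures do not depend on the baseline SD, so the gap to 76 / 84 / 89% becomes about 11 / 5 / 2 points.

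**5. The four-week mean.** Assume a daily SD of 1.7 and equal day-to-day correlation r of 1, 0.7 or 0.5. The SD of the mean is 1.7 × √((1 + 27r)/28) = 1.70 / 1.43 / 1.22. Power at 11 per arm:

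- 2 points is the difference in the mean itself: 75 / 88 / 95%.
- 2 points is a day-28 difference reached linearly over 7 days: mean difference 1.79; 65 / 79 / 90%.
- 2 points is a day-28 difference reached linearly over 14 days: mean difference 1.54; 52 / 67 / 80%.

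A single score gives 75%. The mean may therefore do better or worse than a single score, depending on a time course and an SD that the Protocol does not give.

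**The case against.** The strongest reply is that nothing here is a contradiction. One outcome is labelled primary, change is openly listed as secondary, and the comparison under Patients and protocols simply describes secondary outcomes 1 and 2. The purpose is one line, and the hypothesis beside it (improvement relative to placebo) fits a comparison of mean VAS equally well. Under randomization, level and change of the same follow-up measure target the same effect. This stands: a reader might infer two competing primaries or a biased comparison, and the text supports neither.

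A reader might also infer that the trial is underpowered for its primary. That is not shown. If the 2 points is a true difference in the four-week mean, power at 11 per arm is 75 to 95% over the assumed correlations. The lowest value above, 52%, needs both a 14-day build-up and perfect correlation across 28 days, and neither is in the Protocol.

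A third reply is that adjustment belongs in an analysis plan, and that the stated sentence does not forbid a baseline covariate. In part this stands: the absence of a model for the primary is not a fault here, and the precision figures concern a comparison for which the Protocol makes no power claim. But the Protocol does commit in writing to a pre/post difference between groups. Taken as written, that is the less efficient use of data already in hand.

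Finally, the size of the gain rests on assumed correlations and on equal SDs at the two times. Step 4 shows that it shrinks if the entry rule narrows the baseline.

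**Conclusion.** The point holds in a limited form. The primary is clearly labelled but not carried into the purpose or the described comparison, one term names two measurements, and the 2-point target is attached to neither. These are matters of wording, and they should be settled before any data are seen.

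The substantive gain is in precision. Within a diagnosis, replacing the unadjusted pre/post difference by a comparison adjusted for presentation VAS raises power from about 60/75/83% to about 76/84/89%, for 2 points, SD 1.7 at both times, 11 per arm and assumed correlations of 0.3/0.5/0.6. The gain is smaller if the baseline SD is reduced by the entry rule. Pooled over diagnoses it is about 8 points at a correlation of 0.3 and 2 points or less at 0.5 and 0.6. The direction of any effect on power for the four-week mean is open.

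**What to change.** - **Primary outcome measure:** keep the four-week mean of daily VAS.
- **Purpose and Patients and protocols:** state that the arms are compared on four-week mean daily VAS, adjusted for presentation VAS, and also for diagnosis if the two diagnoses are pooled.
- **Patients and protocols and Secondary outcome measures:** call the clinic reading *week-4 visit VAS* throughout. Make its baseline-adjusted between-arm comparison secondary outcome 1, in place of the pre/post difference.
- **Sample Size:** state that the 2 points is a between-arm difference in the four-week mean, and that SD 1.7, from single presentation scores, stands in for the unknown SD of that mean.

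The cost is wording in these sections and one covariate, which uses one degree of freedom (a second for diagnosis if pooled). Presentation VAS, the visit score and the daily journal are already collected, so no patients or visits are added.

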### **Secondary outcome measures:**

- 1. Pre- to post-treatment difference in VAS score
- 2. Pre- to post-treatment difference in FFI
- 3. Post-treatment FFI at different time points (1, 2, 3, and 4 weeks post treatment)
- 4. Adherence to treatment
- 5. Amount of Chylobinoid cream vs. Placebo cream used during the study period
- 6. Do you believe you received the treatment or placebo? (4 weeks)
- 7. Did the cream we gave you help with your pain? (4 weeks)

# **Procedures for maintaining confidentiality:**

A breach of confidentiality and/or privacy is a risk of this study. To prevent this, all collected data will be stored electronically in password-protected files to protect patient identity and information. All information will be collected and reviewed by the research team only. Data will be maintained on a password-protected computer that will be accessible only to the study team. No patient identifiers will be maintained in the database.

